This pilot study will utilize a single blind, placebo-controlled, randomized, repeated measures experimental design. Participants will be asked to come in for two visits at least 7 days apart. If study procedures are not completed in the two sessions (such as due to equipment malfunction or unexpected time restrictions/events), an additional session may be required to complete procedures. This will be scheduled at the participant's convenience. Participants will be asked to wear comfortable, casual clothing for participation ahead of time, during their phone screening. In the first visit, participants will be asked to complete a demographic health and function questionnaire. Questions may address their injury level, medical history, impact of their condition on physical functioning, breathing function, and their walking or other functional abilities. Participants may then be asked to undergo standardized assessments of muscle strength and sensory function. Following collection of this baseline information, the remainder of the first visit will be similar to all subsequent visits. Visits will include:

- Pre-assessments of respiratory strength, postural strength and function, EMG of trunk muscles, and trunk positioning using non-invasive sensors. For subjects who can stand or walk with assistance, ambulation assessments may be conducted while also recording trunk and lower extremity EMGs, and joint angles or forces using non-invasive sensors.
- 15 short exposures to hypoxic air, or a sham exposure, in a randomized order (details below)
- Post-assessments of respiratory strength, postural function, ambulation, EMG of trunk muscles, and trunk and joint positioning using non-invasive sensors

Each session will last about 3 hours and no longer than 6 hours. Rest breaks will be provided at regular intervals and at any time the participant requests. A study clinician will oversee the study procedures and monitor the participants, including a baseline assessment of vital signs (blood pressure, heart rate, and blood oxygen saturation) for safety.

For participants who provided consent for photography and/or video, recordings or photographs may be obtained during their session. Recordings or photographs will only occur based on the consent provided by each participant. The participant will be informed that they may refuse the use of photography or video recordings at any time during the procedures.

Study Procedures

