- a) Maximum inspiratory pressure – an evaluation of inspiratory respiratory muscle strength, assessed using a digital respiratory pressure meter.
- b) Maximum expiratory pressure – an evaluation of expiratory respiratory muscle strength, assessed using a digital respiratory pressure meter.
- c) Forced vital capacity – The forced vital capacity is an evaluation of how much air a person can forcefully exhale after a maximal inspiratory effort. Tests are conducted using a digital spirometer or respiratory monitor.
- d) Mouth occlusion pressure (P0.1) – P0.1 is an index of the neuromuscular drive to breathe, independent of lung mechanics. Tests are performed by having participants breathe naturally through a mouthpiece with their eyes closed. Upon completion of one breath, at random, the tester manually occludes the mouthpiece for less than half of one second. The pressure generated in the first 0.1 seconds of the participant's initiation of inhalation will be recorded as the participant's P0.1.

3) Standardized assessments of functional ability

3a) Functional ability of the trunk muscles

The degree to which subjects can independently perform certain tasks that require trunk muscles will be assessed with the Neuromuscular Recovery Scale. Four components of this standard, reliable and responsive clinical test of functional ability for people with SCI

will be used (Tester et al., 2016). Standardized instructions will be provided to the subjects for each component. A study staff member trained in administering the Neuromuscular Recovery Scale will supervise testing to ensure proper execution and subject safety. These components include:

- a) Sit – testing the subject's ability to sit tall with proper posture when the feet are flat on the floor.
- b) Reverse Sit-up – subjects will be asked to lower themselves from sitting up to lying supine on a mat as slowly and controlled as possible.
- c) Sit-up – the subject's ability to sit up from lying supine on a table while the feet are on the ground will be assessed.
- d) Trunk extension in sitting – while seated on a table with feet on the floor, subjects will be asked to lean forward with their arms hanging down, and then return to a seated position without using their hands.

3b) Assessment of postural muscle strength in sitting

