A standardized and reliable protocol using a hand-held force dynamometer will be used to assess postural muscle strength for maintaining upright sitting (Larson et al., 2010). A study staff member will apply force to the participant's chest (anterior strength), upper back (posterior strength), or either shoulder (lateral strength) while the participant is asked to resist the force to remain seated, unsupported, on a mat table. The force applied at the point that the participant loses balance or can no longer sit unsupported will be recorded as strength in that direction. This test of seated strength will be carried out by a study staff member experienced in administering the test, and the participant will also be spotted by an additional therapist or research assistant in case the participant is unable to balance themselves during the test.

3c) Assessments of ambulation

These are standard, clinical tests of functional ability that may be used to assess mobility in subjects who can safely attempt these tests. Outcomes from these assessments will allow us to quantify the level of functional mobility of our subjects, and if acute intermittent hypoxia affects levels of functional mobility. These assessments may include:

- a) Timed Up and Go Test – Assessment of walking balance, and fall risk based on the participant's ability to stand up from a seated position, walking 10 meters, turn around and return to the chair and sit down.
- b) 10 meter walk test – Assessment of walking speed over a distance of 10 meters
- c) 30 second chair stand test – Assessment of lower body strength and power in mobility impaired populations, by assessing the maximum amount of times that a participant can safely stand up from a seated position in 30 seconds.

4) EMG activation and activation patterns of respiratory, postural, and lower extremity muscles

Muscle activity will be collected and measured by surface EMG. By analyzing the electrical activity generated during a muscle contraction, EMG analyses allow us to understand timing and amplitude of muscle activation as well as the frequency content of the EMG signal. Thus, we will be able to assess how the nervous system's control of

muscles is disrupted following SCI, and whether this control will be affected by acute intermittent hypoxia.

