Acute intermittent hypoxia is a safe, non-invasive technique to improve muscle strength and activation after SCI. All sessions will be monitored by a study clinician with experience in both delivering acute intermittent hypoxia, and treating individuals with SCI. Hypoxic intervals will be delivered with a commercially available sports performance hypoxicicator. A unit capable of delivering a fraction of inspired oxygen ranging from 21%-9% will be used. Air will be delivered into a mask that will be secured comfortably over the subject's nose and mouth. An SpO₂ sensor that monitors oxygen saturation of the blood will be used to monitor the subject's response to hypoxic intervals; if the user's SpO₂ falls below 80% during a round of hypoxia, the fraction of inspired oxygen delivered by the hypoxicicator will be rapidly increased in order to bring the user's SpO₂ back over the safety threshold. 80% SpO₂ is adequate to induce the effects of hypoxia without causing adverse safety events (Trumbower et al., 2012; Hayes et al., 2014; Lynch et al., 2016; Navarrete-Opazo et al., 2016a, 2016b).

Acute intermittent hypoxia will be provided to the subject by delivering 15 brief exposures (60 to 120 seconds) of hypoxic air alternated with 15 brief exposures (60 to 120 seconds) of room air. The amount of oxygen delivered during hypoxic exposures may range from 15%-9% fraction of inspired oxygen, compared to 21% oxygen in normal atmospheric air. Various protocols have previously used intervals and oxygen concentrations within this range (Trumbower et al., 2012; Tester et al., 2014; Navarrete-Opazo et al., 2016b). To switch from hypoxic to room air, a four-way valve will be attached to the subject's mask which can allow air from the hypoxicator, or ambient air from the room to flow into the mask. The amount of oxygen delivered and the length of the hypoxic and room air exposures will be adjusted during the protocol to maintain safety, tolerability, and a consistent hypoxic response of the subject. The total time of all episodes of alternating room and hypoxic air will be between 30-45 minutes. Alternatively, a sham protocol will be administered in which 21% fraction of inspired oxygen will be delivered by the hypoxicator during hypoxic intervals, and room air will be delivered through the four-way valve during room air intervals.

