Subjects will rest and be asked not to ingest any food or drink other than water for 30 minutes after the delivery of acute intermittent hypoxia, because fullness of the stomach may impede full depression of the diaphragm and compromise maximal respiratory measures. Following this, maximal inspiratory pressure, maximal expiratory pressure, forced vital capacity, mouth occlusion pressure, postural strength assessments, Neuromuscular Recovery Scale components, and assessments of ambulation will be reassessed as outlined above. EMG electrodes, electrogoniometers, and pressure sensors will be worn during the acute intermittent hypoxia and rest period, and will be removed following the conclusion of all testing.

Following the procedures for each visit, a \$75.00 gift card or check will be provided to participants. Thus, upon full completion of two visits, subjects will have been provided with \$150.00 following their participation in the study. If participants are asked to come in for a third session, an additional \$75.00 will be provided.

No standard therapies for people with SCI currently include acute intermittent hypoxia. Thus, this research does not intend to directly deliver therapeutic benefits to subjects. Rather, this research seeks to determine the therapeutic potential of acute intermittent hypoxia on respiratory strength and postural muscle function for people with SCI. As an alternative to participating in this study, subjects may not enroll or choose to withdraw at any time.

Statistical Plan

Percent changes in maximal inspiratory pressure, maximal expiratory pressure, forced vital capacity, mouth occlusion pressure, EMG parameters, spine and hip angles, postural strength measures, absolute Neuromuscular Recovery Scale scores, and assessments of ambulation will be compared pre- and post-intervention for both experimental conditions. Changes for each subject will be averaged, and the group mean change \pm standard deviation will be reported and compared across experimental conditions. Statistical differences between the group means for each variable in each experimental

condition will be compared using t-tests. Multiple comparisons will be accounted for. Statistical analyses will be carried out by the study investigators.

Acute Intermittent Hypoxia Safety Profile

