Some participants may find the mask used during acute intermittent hypoxia uncomfortable, so the mask will be adjusted as necessary to ensure optimal comfort of the subject. Subjects may also feel sleepy during the brief episodes of hypoxia. However, this feeling typically lasts only for the duration of the hypoxic episode, as the episodes of hypoxia are alternated with breathing room air. Additionally, the percent of oxygen delivered will be increased, if necessary, to keep subjects above the safety threshold of 80% SpO₂. All subjects will undergo the acute intermittent hypoxia protocol in a

comfortable chair with armrests and a headrest to ensure both comfort and safety if the subject does become sleepy.

Discomfort and risks of injury from functional assessments are minimal. All procedures are non-invasive and will be supervised by a study clinician with experience in testing breathing, postural muscle strength and function, and ambulation with individuals with SCI. Participants may rest at any time and may opt not to perform any of the study procedures. Participant responses will be closely monitored. During seated tasks of postural muscle function or ambulation, subjects may be assisted as necessary to safely complete the tasks.

The non-invasive sensors affixed with tape or wrapping may cause some mild discomfort or redness. Removal of the tape may be uncomfortable for some participants and participants will be made aware prior to application and removal. Some participants may not be accustomed to the study activities and may become fatigued during the testing. Rest breaks will be provided as needed.

8. Possible Benefits:

Participants may experience short-term improvements in total volume of air breathed in the hours following the procedure. Participants may also experience increased strength in postural muscles in the hours following the procedure. Any responses are not expected to last more than four hours. As these effects have not been tested formally in humans with SCI, responses will likely be variable across participants.

Future populations may benefit from knowledge of how acute intermittent hypoxia affects the outcomes of rehabilitation for people with SCI. Since all risks to the subjects are minimal, the risks are reasonable in relation to the knowledge that could potentially be gained from this pilot study.

9. Conflict of Interest:

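### The plan states only single-blind masking; it does not mask outcome testers, signal processors or analysts, although hand-applied and judged measures carry Aim 2

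*Combined protocol and SAP*

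**What the plan says.** The only description of masking for this trial is in section 6, Overview: "This pilot study will utilize a single blind, placebo-controlled, randomized, repeated measures experimental design". The masked party is not named. Under the heading on delivering the exposure, the sham supplies 21% oxygen from the same device, which fits masking of the participant.

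Staff roles are described in separate places:

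- **Overview:** "A study clinician will oversee the study procedures and monitor the participants".
- **Delivery of the exposure:** "All sessions will be monitored by a study clinician with experience in both delivering acute intermittent hypoxia, and treating individuals with SCI". In the same section: "The amount of oxygen delivered and the length of the hypoxic and room air exposures will be adjusted during the protocol".
- **Section 3a (trunk function):** "The degree to which subjects can independently perform certain tasks that require trunk muscles will be assessed with the Neuromuscular Recovery Scale". A trained staff member supervises this testing.
- **Section 3b (seated strength):** a staff member pushes by hand against the chest, upper back or either shoulder. "The force applied at the point that the participant loses balance or can no longer sit unsupported will be recorded as strength" in that direction.
- **Section 7:** "During seated tasks of postural muscle function or ambulation, subjects may be assisted as necessary to safely complete the tasks".
- **Statistical Plan:** group means in each experimental "condition will be compared using t-tests. Multiple comparisons will be accounted for. Statistical analyses will be carried out by the study investigators".

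The confidentiality section codes participants by study ID and does not mention coding of the condition.

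**The concern.** Each subject is tested before and after both conditions, and the comparison of interest is the change after hypoxia against the change after sham. A tester who knows the condition can influence that comparison through how the push is applied and when balance is judged lost, how a scale item is judged, how much help is given, or how hard a maximal breathing effort is coached. An analyst or signal processor who knows it can be influenced when choosing EMG segments or deciding on exclusions.

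Bias of this kind attaches to the condition itself. Randomising the order balances visit and learning effects but leaves this bias in the hypoxia-minus-sham difference. Specific Aim 2 rests largely on seated dynamometry and the four scale items, which depend most on the person testing. A spurious difference there would misinform whatever work follows this pilot.

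**Working it through.** **Step 1. Who is masked?** The documents were read for any statement on masking, independent assessors or masked analysis. The Overview sentence is the only one about this trial. The other remarks on blinding concern earlier studies. Masking of testers, processors and analysts is therefore unstated.

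**Step 2. Who will know the condition?** In the hypoxia condition, oxygen and interval length are adjusted to the subject's response, and oxygen is raised if SpO2 falls below 80%. In the sham condition the device delivers 21%. Whoever runs the exposure will generally know which it is. A study clinician monitors every session and oversees the procedures; dynamometry and scale testing go to a study staff member. The labels differ, so overlap of roles is possible but not shown. No rule requires separation or stops the condition being passed on to the tester.

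**Step 3. Which outcomes are exposed?**

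| Outcome | Dependence on the tester |
|---|---|
| Seated dynamometry (3b) | High: the tester applies the force and recognises the endpoint |
| Recovery Scale items (3a) | High: items such as good sitting posture or a controlled descent need judgement |
| Ambulation (3c) | Moderate: timed or counted, but help may be given |
| Maximal respiratory tests | Moderate: read digitally, but effort can be coached |
| EMG and angles | Low at recording; open to choices in processing |

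**Step 4. Illustration of scale.** The plan gives no SD, effect size or alpha, so the actual bias cannot be calculated.

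- From the documents: n = 30 (section 6, enrolment target); t-tests (Statistical Plan).
- Assumed: the test is paired, two-sided, at 5%; there is no true effect; tester bias shifts the mean by d SDs of the paired difference.
- Also assumed, since no multiplicity method is named: Bonferroni over eight measures (4 scale items and 4 push directions), giving 0.05/8 = 0.625%.

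The test statistic then follows a noncentral t distribution with 29 degrees of freedom and noncentrality d × √30. For d = 0.2 this is 0.2 × 5.477 = 1.095. The critical values are 2.045 (5%) and 2.949 (0.625%). The probability of exceeding them in either direction is:

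| Shift d | Noncentrality | At 5% | At 0.625% |
|---|---|---|---|
| 0 | 0 | 5.0% | 0.6% |
| 0.1 | 0.548 | 8.3% | 1.4% |
| 0.2 | 1.095 | 18.5% | 4.4% |
| 0.3 | 1.643 | 35.6% | 11.6% |

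A wider family lowers the absolute rates. Adding four respiratory and three ambulation measures makes 8 + 4 + 3 = 15, with a level of 0.05/15 = 0.33% and a critical value of 3.198; d = 0.2 then gives about 2.8%. In each case the rate is several times its nominal level.

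**The case against.** The strongest reply is that this is silence in the plan and not a demonstrated fault. The trial is openly a single-blind pilot, which is a legitimate design, and the role labels for delivery and testing differ. That stands. A reader might infer that the testers will be unmasked, or that one person both delivers and tests; the documents support neither inference.

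The second reply is that safeguards exist: standardised instructions, a trained supervisor for the scale, an experienced tester and an established protocol for dynamometry, and digital reading of the respiratory measures. These narrow the room for bias and deserve credit. They do not replace masking, because a standardised procedure still leaves the push and the judgement with the tester.

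The third reply is that the calculation describes a t-test with 30 subjects and says nothing about how these testers behave. That is correct, and it is why the table is offered only as an illustration. A reader might also quote the unadjusted column alone. The Statistical Plan says multiple comparisons will be accounted for, so the adjusted column belongs beside it. How the scale is analysed, by item or as a total, is not settled either, so no figure specific to the scale is relied on here.

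**Conclusion.** The concern holds as an omission with an open route to bias. Only participant masking can be read from the plan; testers, signal processors and analysts are free to know the condition, and the measures that carry Aim 2 are those most open to a tester's influence. It should be corrected, since the remedy is cheap, but it does not show that results will be biased. Whether testers would know the condition, and how large any effect would be, cannot be determined from the documents.

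The illustrated size (about 19% instead of 5% for a 0.2 SD shift, or about 4.4% instead of 0.6% after adjustment) rests on 30 completing subjects, a paired t-test, an assumed shift and an assumed family of eight.

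**What to change.** 1. **Overview:** state who is masked and who is not, by role.
2. **Statistical Plan:** process EMG and angle files and run the analysis under coded condition labels until the data are locked, with the key held by someone not doing that work. Export only the pre- and post-test segments, because the sensors stay on during the exposure and those recordings could reveal the condition.
3. **Testing procedures:** where feasible with existing staff, have post-exposure dynamometry and scale testing, and preferably the coached respiratory tests and ambulation, done by a staff member who was absent from the exposure and does not know the oxygen setting or the SpO2 readings during it. The 30-minute rest is a natural hand-over, and dynamometry already involves a tester and a second person. Where this is not possible, record who tested and that they were unmasked.

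Safety monitoring, oxygen adjustment and decisions to assist a subject stay as they are.

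**Cost:** a few sentences of text, a key holder, one extra recorded item, and tighter scheduling. The tester is away for about 60 to 75 minutes per visit (30 to 45 minutes of exposure plus 30 minutes of rest), and roles cannot be swapped within a visit. A site that cannot spare the tester needs no extra staff; the possible bias then remains but is disclosed.

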The testing procedures are not particularly strenuous, but could be tiring for some individuals. All participants will be given rest breaks and informed that they may rest or terminate their participation at any time. During brief hypoxic episodes, subjects may become sleepy. If subjects appear to be falling asleep they will be asked to stay awake and report any concerns or feeling of discomfort. The criteria for termination include subject complaints of confusion, dyspnea, onset of angina, and/or atypical bradycardia (drop in heart rate greater than 10 beats per minute). In addition, should the subject's heart rate exceed 70% of their age-predicted maximum (220 – age) then the assessment will halt. In this case, the subject will be asked to rest while blood pressure and heart rate are monitored and will resume only when they return to acceptable values. If any of these conditions persist after rest, the individual's primary physician may be called and referred for evaluation. If the individual complains of angina at rest, loss of consciousness occurs, or cardiac arrest, emergency medical services through 911 will be called immediately.

SpO₂ will be continuously monitored throughout the study. If SpO₂ drops below a safety threshold of 80%, the fraction of inspired oxygen delivered by the hypoxicator will be rapidly increased until the subject is back over 80% SpO₂. This threshold is chosen based

on 80% being the average number the SpO₂ has dropped to in previous studies without any adverse events occurring (Trumbower et al., 2012; Hayes et al., 2014; Lynch et al., 2016; Navarrete-Opazo et al., 2016a). If the subject's SpO₂ remains under 80% or continues to decline after the percent oxygen delivered has been increased, the mask will be removed and the procedure will be aborted. In the event that a subject reports discomfort and does not wish to continue, the mask will be removed and the procedure will be aborted. None of these adverse events are anticipated, however if they occur, each will be handled using the aforementioned methods.

Confidentiality and protecting subject privacy

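### Does the optional extra session leave the analysis with two competing results for one condition?

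*Combined protocol and SAP*

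**What the plan says.** All references are to the combined protocol and SAP.

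- **Overview (6. Research Plan), design:** "This pilot study will utilize a single blind, placebo-controlled, randomized, repeated measures experimental design".
- **Overview, schedule:** "Participants will be asked to come in for two visits at least 7 days apart". If procedures are unfinished, for example after an equipment fault or lack of time, "an additional session may be required to complete procedures. This will be scheduled at the participant's convenience".
- **Overview, content of visits:** after the baseline information is collected, "the remainder of the first visit will be similar to all subsequent visits". The list that follows gives pre-assessments, the hypoxic or sham exposure, and post-assessments.
- **Section on delivering hypoxia or sham:** a third session appears once, as an extra payment equal to that for each planned visit.
- **Statistical Plan:** pre-to-post changes are compared between conditions by t-tests. "Changes for each subject will be averaged, and the group mean change" is then reported with its standard deviation. "Statistical analyses will be carried out by the study investigators".
- **Safety monitoring:** if oxygen saturation stays under the threshold or "continues to decline after the percent oxygen delivered has been increased, the mask will be removed and the procedure will be aborted". No repeat is mentioned.
- **8. Possible Benefits:** "Any responses are not expected to last more than four hours".

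**The concern.** The sponsor foresees a third session and has set a payment for it, but gives no rule for its data. If the session is a full visit, the repeated condition could carry two sets of changes, at least one of them partial. An analyst could keep the first, keep the later, or average them. The sentence about averaging changes does not settle this, because it most naturally means averaging over participants.

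The setting makes the gap look worse. The trial is single blind, the investigators do the analysis, and no passage says that they are masked. Whoever chooses between two sets of changes could know both the condition and the results. If exposures aborted for low saturation also led to extra sessions, repeats would fall mainly on the hypoxia condition. At stake would be a hypoxia–sham difference that depends on the analyst, and in the worst case one tilted towards hypoxia.

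**Working it through.** **Step 1: when do two changes compete?** The document gives no frequency for extra sessions, so the first check is by case.

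| Use of the extra session | Changes available per test for that condition |
|---|---|
| Finishing baseline items (questionnaire, neurological examination) | One; outcome data untouched |
| First attempt stopped before the exposure | One, from the extra session; the first attempt has no post-test |
| First attempt stopped part-way through post-tests, then a full visit | One for each test missed the first time; two only for a test already finished and then redone |
| Post-tests alone on a later day, no new exposure | One from the first attempt for finished tests; the late post-tests lie beyond the four hours in section 8 and do not measure the response |

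Only part of the third row offers a choice. The Overview says that all visits share the pre-test, exposure and post-test sequence, and the analysis variable is a pre-to-post change. The natural unit is therefore a pre/post pair from one session.

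**Step 2: does the choice of convention matter?** Inputs:

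- n = 30, the enrolment target in the Research Plan.
- k participants with a second hypoxia change. The values k = 1, 3, 6 are assumed.
- Changes independent and normal, SD 1, no true effect (assumed).
- Two-sided paired t-test at 5% (assumed; the Statistical Plan says only t-tests and gives no level).

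The expected larger value of two independent standard normals is 1/√π = 0.564. If the larger hypoxia change is kept for k participants, the bias in the mean difference is 0.564 × k/30:

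- k = 1: 0.564 × 1/30 = 0.019 SD
- k = 3: 0.564 × 3/30 = 0.056 SD
- k = 6: 0.564 × 6/30 = 0.113 SD

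The standard error of the mean difference is √(2/30) = 0.258 SD, so these biases are 0.07, 0.22 and 0.44 standard errors.

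Simulated rejection rates (200,000 replicates per setting):

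| Convention | k | Upper tail | Two-sided |
|---|---|---|---|
| No repeats | 0 | 2.5% | 5.0% |
| First value, or mean of both | 1, 3, 6 | 2.5% | 5.0–5.1% |
| Larger hypoxia value | 1 | 2.9% | 5.0% |
| Larger hypoxia value | 3 | 4.0% | 5.4% |
| Larger hypoxia value | 6 | 6.0% | 6.8% |

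Keeping the later value gives the same nominal rates as keeping the first. All three conventions that an analyst might reasonably adopt are therefore valid; the inflation comes only from selecting on the outcome.

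**Step 3: is the worst case realistic?** It assumes that two complete changes exist, which Step 1 shows to be the exception. It also assumes that they are independent. Two changes from the same person under the same condition would probably be correlated. At a correlation of 0.5 the upper tail is about 2.8%, 3.5% and 4.7% for k = 1, 3, 6, and the two-sided rate about 5.0%, 5.2% and 5.8%. If repeats are equally common in both conditions and the larger value is kept in each, the bias is about zero.

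**Step 4: the aborted exposure.** The Overview's examples of unfinished procedures are equipment faults and time limits. Safety monitoring ends the procedure and says nothing about another attempt. The two sections do not contradict each other, and neither supports the idea that aborted hypoxia sessions are repeated.

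**The case for a change.** The best case for a change is that the event is foreseen, the rule is missing, and one sentence would supply it. Pilot status does not supply the rule. With 30 participants a few discretionary choices can move an estimate, and nothing in the document stops an unmasked investigator from making them after seeing the data.

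Some of this stands. The rule is absent, the extra session's condition and spacing are not stated, and writing down a convention before outcomes are seen would do no harm. It does not amount to a needed change, for three reasons. First, the plan does not direct outcome-based selection, and analyst masking is a general matter that this sentence neither creates nor cures. Second, every convention that ignores the outcomes preserves the error rates, so the plan gives no wrong answer as written. Third, a stricter rule could do damage. Requiring every planned test in one session is hard to apply when participants may decline any test. It would also discard a test validly finished only in the extra session. Requiring a completed exposure could remove hypoxia sessions more often than sham ones. The convention that avoids these problems, the first same-session pre/post pair for each test, is the one the visit structure already suggests.

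**Conclusion.** No change follows. The document leaves a data-handling detail unwritten for a contingency of unknown frequency, and the visit sequence together with the expected duration of response points an analyst to a sensible default. Under any convention that ignores outcomes the effect on error rates is nil. Under deliberate selection of the larger hypoxia change it is at most 0.11 SD of bias and a 6.8% two-sided error for as many as 6 of 30 participants, and at k = 1 the two-sided rate is unchanged.

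These figures rest on assumed values of k, a paired test at the 5% level, normal and independent changes with equal SDs, and repeats in the hypoxia condition only. The Statistical Plan's undertaking to allow for multiple comparisons is not modelled. The conclusion would need another look if extra sessions proved common and were concentrated in one condition. Nothing in the document indicates that.
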